16.1 Discontinuation of Study Intervention

Participants will be withdrawn from treatment for any of the following reasons:

- A participant may withdraw from the study at any time, at his/her own request (ie, withdrawal of consent), and without giving a reason.
- Occurrence of an exclusion criterion, which is clinically relevant and affects the participant's safety, if discontinuation is considered necessary by the Investigator.

The participant may be withdrawn at any time at the discretion of the Investigator for safety, behavioral, compliance, or administrative reasons.

- Confirmed PD per RECIST 1.1 with the exception that participants receiving treatment may continue past PD if the participant's ECOG PS has remained stable, and if in the opinion of the Investigator, the participant will benefit from continued treatment.
 - Some ADRs require withdrawal from treatment.
 - Drug must not be given to a known pregnant participant.
- Use of a nonpermitted concomitant drug (without approval of MD Anderson and the Medical Monitor provided by the IND office), as defined in dedicated sections of this protocol, where the predefined consequence is withdrawal from the study intervention.

16.2 Participant Discontinuation/Withdrawal from the Study

A participant must be withdrawn in the event of any of the following:

- A participant may withdraw from the study at any time, at his/her own request (ie, withdrawal of consent), and without giving a reason.
- The participant may be withdrawn at any time at the discretion of the Investigator for safety, behavioral, compliance, or administrative reasons.

In case of withdrawal from treatment, the day of End-of-Treatment will correspond to the day of withdrawal (or within 7 days).

17 Lost to Follow-up

A participant will be considered lost to follow-up if he or she repeatedly fails to return for scheduled visits and is unable to be contacted by the study site.

The following actions must be taken if a participant fails to return to the clinic for a required study visit:

- The site must attempt to contact the participant and reschedule the missed visit as soon as possible, counsel the participant on the importance of maintaining the assigned visit schedule, and ascertain if the participant wants to or should continue in the study.
- Before a participant is deemed “lost to follow-up”, the Investigator or designee must make every effort to regain contact with the participant: 1) where possible, make 3 telephone calls; 2) if necessary, send a certified letter (or an equivalent local method) to the participant’s last known mailing address, and 3) if a participant has given the appropriate consent, contact the participant’s general practitioner for information. These contact attempts should be documented in the participant’s medical record.
- Should the participant continue to be unreachable, he/she will be considered to have withdrawn from the study.

18 Long-term follow-up

After the End of Treatment evaluation, information on additional oncologic treatment (including post-operative systemic therapy and radiation therapy), time to disease progression/recurrence, sites of recurrence, development of second primary tumors, additional therapy for recurrence, long-term survival, and other relevant clinical data will be obtained. Patients (or their family members or designees) may be contacted by telephone or in writing or by electronic mail or during clinic visits after treatment discontinuation for collection of long-term follow-up data. Long-term follow-up clinical information may also be obtained through chart reviews. Long-term follow up will be conducted as long as needed to obtain relevant information for accurate interpretation of the study, but for no longer than five years.

19 Data Sharing

Researchers can do more powerful studies when they share with each other the information they get from studying human samples. NGS data may be placed in a local M.D. Anderson Institutional Data Repository, commonly referred to as BigData; where both deposition of and access to data require governance and approval. In some cases, grant requirements may require deposition of large-scale data into the public Genotypes and Phenotypes database (dbGaP) an access controlled database overseen by the National Center for Biotechnology Information (NCBI). In other cases peer reviewed Journals may require data to be shared through a resource such as dbGaP. Data submitted to those repositories will only be shared in a de-identified fashion and without associated clinical data or identifiers. This data will be used only for research purposes, and the data elements collected and analyzed will only be those that are necessary to conduct this research.

Database access additional protections: The precedent to publically broadcast sequence data has been set by large consortial projects, such as The Cancer Genome Atlas (TCGA) and the Encyclopedia of DNA Elements (ENCODE), in order to maximize data utility. However, we know

there is the potential for privacy risks associated with the release of sequence data to databases and while the risk may be small, it could grow in the future as technology advances. To minimize this potential, we will implement good faith efforts to ensure patient confidentiality and reduce patient exposure. The database of Genotypes and Phenotypes and others like it are extremely access restricted. Only authorized researchers may deposit or access the data and either or both efforts require MD Anderson institutional approval. Sequence data will only be broadcast through secure transmission processes. All samples will be de-identified with access to the linking table available only to the MD Anderson PI and his/her designees. Only non- identifiable data will be deposited to dbGaP i.e., no linking table or access to a linking table will be available. Research records will be kept separate from medical records and patients will not have access to any of the research data.

Protected health information (PHI) may be collected from medical records that are related to health and/or disease history including test results, medical procedures, and images (such as X-rays) in addition demographic and environmental factors may be requested. Researchers will use this information to better understand how genes affect health and response to treatment. All samples will be de-identified with access to the linking table available only to the MD Anderson PI and his/her designees.

20 Study Medication - Pharmaceutical Formulation

Pharmaceutical Properties and Description of the Formulation M7824
drug product is provided as either a sterile liquid formulation.

The Concentrate for Solution for Infusion (liquid formulation) is packaged at a 10 mg/mL concentration in USP / Ph. Eur. type I 50R or 20R vials which are filled with drug product solution to allow an extractable volume of 60 mL (600 mg/60 mL) or 20 mL (200 mg/20 mL), respectively. The vials are closed with rubber stoppers with the same composition as used for freeze-dried formulation, but in serum format complying with USP and Ph. Eur. with an aluminum crimp seal closure.

The excipients are viewed as standard, and therefore, not a safety risk. The estimated volumes of delivery are anticipated to be no more than 250 mL, which are clinically acceptable.

20.1 Study Medication - Handling of the Dosage Form

For applications in clinical studies the liquid formulation is diluted directly with 0.9% saline solution. The estimated volumes of delivery are anticipated to be no more than 250 mL, which are clinically acceptable. Detailed information on infusion bags and medical devices to be used for the preparation of the dilutions and subsequent administration will be provided in the manual of preparation.

20.2 Study Medication - Instructions for Storage

M7824 drug product must be stored at 2°C to 8°C until use. The storage condition is based on data from ongoing long term stability studies with M7824.

M7824 drug product stored at room (23°C to 27°C) or higher temperatures for extended periods of time might be subject to degradation. For application in clinical studies, the liquid formulation is diluted directly with 0.9% saline solution.

The chemical and physical in-use stability for the infusion solution of M7824 in 0.9% saline solution has been demonstrated for a total of 72 hours at 2°C to 8°C and 24 hours at room temperature. However, from a microbiological point of view, the diluted solution should be used immediately and is not intended to be stored unless dilution has taken place in controlled and validated aseptic conditions. If not used immediately, in-use storage times and conditions prior to administration are the responsibility of the user. Do not freeze or shake the diluted solution.

No other drugs should be added to the infusion containers containing M7824.

21 STUDY ASSESSMENTS AND PROCEDURES

Baseline evaluation:

Investigations	Timing		
History and Physical Exam including:	Treatment history Medical history Smoking history Height and weight	Vital signs ECOG PS TNM stage	Within 14 days prior to treatment initiation
Current Smoking Status and Tobacco Use	Assessment of patient's current smoking status and tobacco use		Within 14 days prior to treatment initiation
Symptoms & Toxicities	Evaluation and documentation of symptoms and toxicities using the NCI CTCAE v5.0		Within 14 days prior to treatment initiation
Concomitant Medications	Documentation of concomitant medications		Within 14 days prior to treatment initiation
Hematology and Coagulation	CBC with hemoglobin, platelets, and WBC with differential Prothrombin time (PT) / Partial thromboplastin time (PTT)		Within 14 days prior to treatment initiation
Biochemistry	Albumin Alkaline phosphatase Potassium Total bilirubin, direct, indirect BUN Creatinine Total protein Free T4, TSH	Glucose LDH SGOT (AST) SGPT (ALT) Sodium Magnesium Uric acid	Within 14 days prior to treatment initiation

Pregnancy Test	Urine or serum (for women of childbearing potential only)	Within 48 hours prior to treatment initiation
Radiology	CT chest	Within 30 days prior to treatment initiation
Radiology	PET-CT	Within 60 days prior to treatment initiation
Radiology	MRI brain or CT brain (only for patients with stage II or III on pre-operative staging)	Within 60 days prior to treatment initiation
Mediastinal staging	CT chest / PET-CT, mediastinoscopy, and/or endobronchial ultrasound	Within 60 days prior to treatment initiation
Pulmonary tests	Complete pulmonary function test	Within 60 days prior to treatment initiation
Tumor/Adjacent Lung Tissue Collection for Biomarkers	Archival tissue or new biopsy of primary tumor for biomarker analysis (optional) Tissue obtained for mediastinal staging (optional)	Prior to treatment initiation
Blood-based biomarkers	Blood sample	Prior to treatment initiation
Stool-based Microbiome	Stool sample	Prior to treatment initiation
Pharmacokinetic (PK) studies	Blood sample	Prior to infusion and immediately after infusion of dose #1 of M7824
Anti-Drug Antibodies (ADA) studies	Blood sample	Prior to infusion of dose #1 of M7824

Evaluation during neoadjuvant treatment (prior to each M7824 infusion):

Investigations		Timing	
Physical Exam Including:	BSA Vital signs	Within 7 days prior to dose #2 and #3 of M7824	
Hematology	CBC with hemoglobin, platelets, and WBC with differential	Within 7 days prior to dose #2 and #3 of M7824	
Pregnancy Test	Urine or serum (for women of childbearing potential only)	Within 7 days prior to dose #2 and #3 of M7824	
Biochemistry ¹	Albumin Alkaline phosphatase Total bilirubin, direct, indirect BUN Creatinine Total protein Free T4, TSH	Glucose LDH Potassium SGOT (AST) SGPT (ALT) Sodium Magnesium Uric acid	Within 7 days prior to dose #2 and #3 of M7824
Radiology ¹	CT chest PET-CT	At least 14 days after the last dose of M7824	
Symptoms & Toxicities	Evaluation and documentation of symptoms and toxicities using the NCI CTCAE v5.0	On an ongoing basis throughout the study until the final study visit	
Concomitant Medications	Documentation of concomitant medications	On an ongoing basis throughout the study until the final study visit	
Blood-based biomarkers ¹	Blood sample	Within 7 days prior to dose #2 and #3 of M7824 and at least 14 days after the last dose of M7824	

Pharmakokinetic (PK) studies	Blood sample	Prior to infusion of dose # 2 Prior to infusion and immediately after infusion of dose #3 At least 14 days after the last dose of M7824
Anti-Drug Antibodies (ADA) studies	Blood sample	Prior to infusion of dose #3 of M7824 At least 14 days after the last dose of M7824
Pulmonary tests	Complete pulmonary function test ²	At least 14 days after the last dose of M7824
Stool-based Microbiome	Stool sample	At least 14 days after the last dose of M7824
¹ If information / studies have already been obtained but therapy is delayed for any reason, repeated studies are not necessary prior to next cycle of therapy. ² Complete pulmonary function test may not be required if patient is no longer considered a surgical candidate post neoadjuvant therapy based on the treating physician's discretion.		

Assessments at surgery:

Investigations	Timing
Surgical procedure	Title of operation Status of resection margins (R0, R1, R2)
Tumor Tissue Collection	ypTNM Major pathologic response Percentage of viable tumor cells Nodal stations dissected / sampled and nodal status (positive vs. negative) at each station Evaluation of extra-capsular nodal spread

End of treatment assessments:

Investigations		Timing
Physical Exam Including:	Vital Signs	Approximately within 8 weeks after surgery
Blood-based biomarkers	Blood sample	Approximately within 8 weeks after surgery
Symptoms & Toxicities	Evaluation and documentation of symptoms and toxicities using the NCI CTCAE v5.0 Retrospective evaluation of any	Approximately within 8 weeks after surgery

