Embryofetal toxicities are a known risk of the PD-1 / PD-L1 targeting class. Animal models link the PD-1 / PD-L1 signaling pathway with maintenance of pregnancy through induction of maternal immune tolerance to fetal tissue. Based on its mechanism of action (MoA), M7824 may cause fetal harm when administered to a pregnant female. An appropriate contraception warning is provided in this clinical protocol. Subjects with pregnancy or in lactation period are prohibited from being enrolled in clinical trials.

Mild to Moderate Mucosal Bleeding Events

Mucosal bleeding events of mild to moderate severity were observed in participants treated with M7824 in ongoing studies and are a potential risk for M7824. Events may include epistaxis, hemoptysis, gingival bleeding, or hematuria among others. In general, majority of these events were observed to be self-limiting, did not require intervention, and resolved without discontinuation of study treatment.

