20. Patients who are sexually active, with preserved reproductive capacity, and unwilling to use a medically acceptable method of contraception (e.g. such as implants, injectables, combined oral contraceptives, some intrauterine devices or vasectomized partner for participating females, condoms for participating males) during and after the trial as detailed below:

- a. WOCPB should use an adequate method to avoid pregnancy for 65 days after the last dose of investigational drug.
- b. Men who are sexually active with WOCPB must use any contraceptive method with a failure rate of less than 1% per year.
- c. Men receiving immunotherapy and who are sexually active with WOCPB will be instructed to adhere to contraception for a period of 125 days after the last dose of investigational product.
- d. Women who are not of childbearing potential as well as azoospermic men do not require contraception.

21. Psychological, familial, sociological or geographical factors potentially hampering compliance with the study protocol and follow-up schedule.

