11.7.5 Pharmacokinetics and Anti-Drug Antibody

To evaluate population steady-state concentrations (PK) and potential development of anti-drug antibody (ADA), blood will be collected at the following timepoints as sponsor's lab manual.

Pharmacokinetics Samples:

- a) PK 1 - Dose #1 M7824: Prior to infusion of Dose #1 (60 minutes prior to infusion)
- b) PK 2 - Dose #1 M7824: immediately after infusion (within 60 minutes after infusion)
- c) PK 3 - Dose #2: Prior to infusion Dose #2 (60 minutes prior to infusion)
- d) PK 4 - Dose #3 M7824: Prior to infusion Dose #3 (60 minutes prior to infusion)
- e) PK 5 - Dose #3 M7824: immediately after infusion Dose #3 (within 60 minutes after infusion)
- f) PK 6 - at least 14 days after Dose #3

Anti-Drug Antibody samples:

- g) ADA 1 - Dose #1 M7824: Prior to infusion of Dose #1 (60 minutes prior to infusion)
- h) ADA 2 - Dose #3 M7824: Prior to infusion Dose #3 (60 minutes prior to infusion)
- i) ADA 3 - at least 14 days after Dose #3

12. Study Intervention(s) Preparation, Handling, Storage, and Accountability

Further guidance and information for the preparation, handling, and storage of study intervention(s) are provided in the Pharmacy Manual.

The Investigator and MD Anderson Cancer Center are responsible for study intervention accountability, reconciliation, and record maintenance (ie, receipt, reconciliation, and final disposition records).

- Upon receipt of the study intervention(s), the Investigator or designee must confirm appropriate temperature conditions have been maintained during transit and any discrepancies are reported and resolved before use. Also, the responsible person will check for accurate delivery and acknowledge receipt by signing or initialing and dating the appropriate document and returning it to the location specified. A copy will be archived for the Investigator Site File.
- Only participants enrolled in the study may receive study intervention(s) and only authorized site staff may supply or administer it. All study intervention(s) must be stored in a secure, environmentally-controlled, and monitored (manual or automated) area, in accordance with the labeled storage conditions, and with access limited to the Investigator and authorized site staff.
- Dispensing will be recorded on the appropriate accountability forms so that accurate records will be available for verification at each monitoring visit.

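### Before doses 2 and 3 the pregnancy test may be 7 days old, 4 to 5 days looser than the 48 or 72 hours allowed before dose 1, and the protocol gives no reason

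*Combined protocol and SAP*

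**What the plan says.** The protocol sets the pregnancy test window in three places, each for women of childbearing potential and each accepting urine or serum.

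- Section 21, baseline evaluation: "Within 48 hours prior to treatment initiation".
- Section 10.2, exclusion criterion 9: a negative test no more than 72 hours before immunotherapy starts.
- Section 21, evaluation during neoadjuvant treatment: "Within 7 days prior to dose #2 and #3 of M7824". The physical exam, hematology and biochemistry rows of that table carry the same timing.

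Section 5.1 states the hazard: "M7824 may cause fetal harm when administered to a pregnant female". Section 16.1 bars giving the drug to a participant known to be pregnant. Appendix 2 (Pregnancy and Reporting) requires permanent discontinuation and notification within 24 hours if a pregnancy is found. On contraception, Section 10.2 says: "WOCPB should use an adequate method to avoid pregnancy for 65 days after the last dose of investigational drug". Section 15.2 calls for highly effective contraception in participants able to conceive.

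**The concern.** The rule against dosing in pregnancy protects a participant only as well as her pregnancy status is known at the infusion. At baseline the protocol treats this test differently from routine laboratory work: blood tests may be up to 14 days old, the pregnancy test only 48 hours. Before doses 2 and 3 that distinction disappears, and the pregnancy test takes the same 7-day window as hematology and biochemistry. No reason is given for accepting an older result at the later doses, although the drug and the hazard are the same.

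What is at stake is individual safety. A site that follows Section 21 exactly may infuse dose 2 or 3 on a week-old negative result. A pregnancy that became detectable after that test would not be known when the drug is given. The primary endpoint, the sample size and the toxicity boundaries are not touched.

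**Working it through.** The plan states no derived figure on this point, so there is none to reproduce. The check is a comparison of windows and some day arithmetic.

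**Inputs**

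- Window before dose 1: 48 hours = 2 days (Section 21, baseline table), or 72 hours = 3 days (Section 10.2, exclusion criterion 9).
- Window before doses 2 and 3: 7 days (Section 21, on-treatment table).
- Dosing: nominal days 1, 15 and 29 (Section 9.1), every 14 days with a tolerance of 3 days either way (Synopsis).

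**Step 1. How much looser are the later doses?** Difference = later window − dose 1 window.

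- Against the schedule: 7 − 2 = 5 days.
- Against the eligibility rule: 7 − 3 = 4 days.

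**Step 2. How early in the dosing interval can a compliant test be taken?** Earliest day after the previous dose = interval − window. The interval runs from 14 − 3 = 11 to 14 + 3 = 17 days.

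| Interval | 7-day window | 72-hour window | 48-hour window |
|---|---|---|---|
| 11 days | 11 − 7 = day 4 | 11 − 3 = day 8 | 11 − 2 = day 9 |
| 14 days (nominal) | 14 − 7 = day 7 | 14 − 3 = day 11 | 14 − 2 = day 12 |
| 17 days | 17 − 7 = day 10 | 17 − 3 = day 14 | 17 − 2 = day 15 |

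At the nominal interval the test may be taken halfway between two doses (7 / 14 = 0.5).

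**Step 3. Does the delay waiver stretch the window?** Footnote 1 of the on-treatment table says that, if therapy is delayed, "repeated studies are not necessary prior to next cycle of therapy". Its marker stands on the biochemistry, radiology and blood-biomarker rows, not on the pregnancy row. A delayed dose therefore still needs a test no more than 7 days old, and 7 days is the true maximum.

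**Step 4. Do the two dose 1 windows conflict?** A test within 48 hours satisfies both. A test 49 to 72 hours old satisfies the eligibility criterion but not the schedule. The mismatch is small and does not alter the main comparison, because 7 days is looser than either.

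**Step 5. Is there an existing contact for a later test?** Section 11.7.5 already schedules a pharmacokinetic sample 60 minutes before doses 2 and 3, so the participant is on site before the infusion.

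**The case against.** The strongest reply is that this is a preference. No section sets a maximum age for an on-treatment test, and whether 7 days is too long is a clinical judgement. The existing protection is layered: pregnant women are excluded, contraception is required, a test precedes each of only three doses, dosing in known pregnancy is barred, and Appendix 2 governs any pregnancy that is found. A shorter window also cannot detect a conception too recent for any test. All of this stands, and it keeps the gain small. None of it explains why the later doses should have a looser window than either of the dose 1 windows.

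A reader might also infer that a test is missing after treatment, because the pregnancy row ends with dose 3 while imaging, biomarker blood, pharmacokinetic, anti-drug-antibody, lung-function and stool rows have a time point "At least 14 days after the last dose of M7824". The documents do not support treating that as a gap:

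- The table is headed as assessments before each infusion. Physical exam, hematology and biochemistry stop at dose 3 as well.
- No M7824 follows dose 3, so a later test would gate no study drug.
- The end-of-treatment table is cut off in the available text, so absence from the whole schedule cannot be established.
- Routine care before a scan or operation may already include a test.
- Nothing in the table places the blood draw before the PET-CT, so a test ahead of the scan without a further visit is not shown to be feasible.

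**Conclusion.** The point holds as a minor safety refinement. Before doses 2 and 3 the accepted test age is 5 days longer than the dose 1 schedule and 4 days longer than the eligibility criterion, without a stated reason. A compliant test can fall as early as day 4 to 10 after the previous dose; a 48-hour window would move that to day 9 to 15.

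It would be too strong to call this an error or a contradiction, since different windows at different doses can coexist and no stated standard is breached. The size rests on the Synopsis tolerance of 3 days around a 14-day interval. The number of women of childbearing potential among the 23 planned patients is not given and may be zero. No endpoint or analysis depends on the change.

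**What to change.** In both tables of Section 21, require for women of childbearing potential a negative urine or serum pregnancy test within 48 hours before each of doses 1, 2 and 3, and state that a urine test on the infusion day is enough. Change exclusion criterion 9 in Section 10.2 from 72 to 48 hours, so that eligibility and schedule agree. No post-treatment test needs to be added on this ground.

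The number of scheduled tests stays at three, and an infusion-day test needs no extra visit. The cost is practical: before doses 2 and 3 the test can no longer be combined with laboratory work done up to a week earlier, and staff must read the result before starting the infusion.
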